## 2. STUDY OBJECTIVES AND ENDPOINTS

OBJECTIVES	ENDPOINTS
Primary	
To assess the effect on respiratory drive of morphine administered after multiple doses of AZD4041 compared to morphine administered alone in healthy recreational opioid users	
 
EtCO2 (mmHg): Incidence of increased EtCO2 of at least 10 mmHg compared to baseline or >50 mmHg (sustained for at least 30 seconds)
 
SpO2 (%): Incidence of reduction in SpO2 to <92% (sustained for at least 30 seconds)
 

Secondary	
To assess the safety and tolerability of multiple doses of AZD4041 when co-administered with a single dose of morphine in healthy recreational opioid users	
 
SpO2 (%)
 
Mean time to reduction in SpO2 to <92% (sustained for at least 30 seconds)
 
Mean duration of reduction in SpO2 to <92%
 

	(sustained for at least 30 seconds)
	
 
Maximum postdose reduction of SpO2 adjusted for baseline
 

	
 
Mean postdose SpO2
 

	• EtCO 2 (mmHg)
	
 
Mean time to each increased EtCO2 episode of at least 10 mmHg compared to baseline or >50 mmHg (sustained for at least 30 seconds)
 

	
 
Mean duration of each increased EtCO2 episode of at least 10 mmHg compared to baseline or >50 mmHg (sustained for at least 30 seconds)
 

	
 
Maximum postdose increase in EtCO2 adjusted for baseline
 

	
 
Mean postdose EtCO2
 

	Respiratory rate (breaths/min)
	
 
Incidence of reduced respiratory rate to <6 breaths/min (sustained for at least 30 seconds)
 

	
 
Mean time to each reduced respiratory rate episode of <6 breaths/min (sustained for at least 30 seconds)
 

	
 
Mean duration of each reduced respiratory rate episode of <6 breaths/min (sustained for at least 30 seconds)
 

	
 
Maximum postdose decrease in respiratory rate adjusted for baseline
 

OBJECTIVES	ENDPOINTS
	
 
Mean postdose respiratory rate
 

	• Incidence, frequency, severity, and relationship of AEs
	• Vital signs (blood pressure, heart rate, and oral temperature)
	• ECGs (12-lead safety ECGs, 12-lead digital ECGs, and ECG telemetry)
	• Clinical laboratory test results (clinical chemistry, hematology, coagulation, urinalysis)
	Physical examination findings

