## 8.5. Determination of Sample Size

No formal sample size calculation has been performed. The number of participants is based on the precedent set by other studies of similar nature (Verbekt et al, 2017). The number of

participants planned for completion in this study is considered sufficient to achieve the study objectives. Approximately 44 subjects will be randomized (28 AZD4041 + morphine and 16 Placebo + morphine) to complete at least 36 subjects (24 AZD4041 + morphine, and 12 Placebo + morphine on Day 15).

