2 STUDY OBJECTIVES

The objectives of the study and corresponding study endpoints are detailed in [Table 2-1](#).

Table 2-1 Objectives and Related Endpoints

Objective	Endpoint
Primary	
To assess the effect on respiratory drive of morphine administered after multiple doses of AZD4041 compared to morphine administered alone in healthy recreational opioid users	
 • EtCO₂ (mmHg): Incidence of increased EtCO₂ of at least 10 mmHg compared to baseline or >50 mmHg (sustained for at least 30 seconds) • SpO₂ (%): Incidence of reduction in SpO₂ to <92% (sustained for at least 30 seconds)
Secondary	
 • SpO₂ (%) ▪ Mean time to reduction in SpO₂ to <92% (sustained for at least 30 seconds) ▪ Mean duration of reduction in SpO₂ to <92% (sustained for at least 30 seconds) ▪ Maximum postdose reduction of SpO₂ adjusted for baseline ▪ Mean postdose SpO₂ • EtCO₂ (mmHg) ▪ Mean time to each increased EtCO₂ episode of at least 10 mmHg compared to baseline or >50 mmHg (sustained for at least 30 seconds) ▪ Mean duration of each increased EtCO₂ episode of at least 10 mmHg compared to baseline or >50 mmHg (sustained for at least 30 seconds) ▪ Maximum postdose increase in EtCO₂ adjusted for baseline ▪ Mean postdose EtCO₂

	
 • Respiratory rate (breaths/min) ▪ Incidence of reduced respiratory rate to <6 breaths/min (sustained for at least 30 seconds) ▪ Mean time to each reduced respiratory rate episode of <6 breaths/min (sustained for at least 30 seconds) ▪ Mean duration of each reduced respiratory rate episode of <6 breaths/min (sustained for at least 30 seconds) ▪ Maximum postdose decrease in respiratory rate adjusted for baseline ▪ Mean postdose respiratory rate • Incidence, frequency, severity, and relationship of AEs • Vital signs (blood pressure, heart rate, and oral temperature) • ECGs (12-lead safety ECGs, 12-lead digital ECGs, and ECG telemetry) • Clinical laboratory test results (clinical chemistry, hematology, coagulation, urinalysis) • Neurological examination findings • Columbia Suicide Severity Rating Scale (C-SSRS) findings • Physical examination findings • Type of medical intervention used, summarized for each event of significantly increased EtCO₂, reduced SpO₂, or reduced respiratory rate

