9 SAFETY ANALYSIS

9.1 Respiratory Depression Analysis

Summary statistics and inferential analysis for respiratory depression endpoints will be presented for all subjects who completed all EtCO₂ assessments in addition to the Safety Population, when possible. Incidence of increased EtCO₂ of at least >50 mmHg will be summarized by treatment and time point using frequency tables. Mean time to each increased EtCO₂ episode of at least >50 mmHg, mean duration of each increased EtCO₂ episode of at least >50 mmHg, and mean postdose EtCO₂ will be summarized by treatment and time point using descriptive statistics.

Maximum postdose increase in EtCO₂ E_{max} (postdose – predose) will be summarized by treatment using descriptive statistics and inferential analysis. EtCO₂ averages (predose average from Days 2 to 15), and postdose average on Day 15 will also be summarized by treatment using descriptive statistics and inferential analysis. For each event of significantly increased ETCO₂, type of medical intervention used will be listed.

Incidence of reduction in SpO₂ to <92% will be summarized by treatment and time point using frequency tables. Mean time to reduction in SpO₂ to <92%, mean duration of reduction in SpO₂ to <92%, and mean postdose SpO₂ will be summarized by treatment and time point using descriptive statistics. Maximum postdose reduction of SpO₂ E_{max} (predose – postdose) will be summarized by treatment using descriptive statistics and inferential analysis. SpO₂ averages (predose average from Days 2 to 15), and postdose average on Day 15 will also be summarized by treatment using descriptive statistics and inferential analysis. For each event of significantly reduced SpO₂, type of medical intervention used will be listed.

Incidence of reduced respiratory rate to <6 breaths/min will be summarized by treatment and time point using frequency tables. Mean time to each reduced respiratory rate episode of < 6 breaths/min, mean duration of each reduced respiratory rate episode of <6 breaths/min, and mean postdose respiratory rate will be summarized by treatment and time point using descriptive statistics. Maximum postdose decrease in respiratory rate E_{max} (predose – postdose) will be summarized by treatment using descriptive statistics and inferential analysis. Respiratory rate averages (predose average from Days 2 to 15), and postdose average on Day 15 will also be summarized by treatment using descriptive statistics and inferential analysis.

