For EtCO₂, SpO₂, and respiratory rate the following figures will be generated:

- 1) Sequence 1: Mean (\pm SD) treatment by time point for Day 1 Morphine alone matched to Day 15 Morphine + AZD4041
- 2) Sequence 2: Mean (\pm SD) treatment by time point for Day 1 Morphine alone matched to Day 15 Morphine + Placebo
- 3) Mean (\pm SD) treatment by time point for Days 2-15 predose AZD4041 vs. Days 2-15 predose Placebo
- 4) Boxplot for E_{max} Day 1 Morphine alone matched to Day 15 Morphine + AZD4041
- 5) Boxplot for E_{max} Day 1 Morphine alone matched to Day 15 Morphine + Placebo
- 6) Boxplot for E_{max} Day 15 Morphine + AZD4041 vs. Day 15 Morphine + Placebo

For all inferential analysis on EtCO₂, SpO₂, and respiratory rate, mixed-effects models will be used for E_{max} and averaged measures. The models will include sequence, time (as a ordered factor variable), and the sequence-by-time interaction as fixed effects and baseline as a covariate, with 95% confidence intervals reported along with p-values. Homogeneity of treatment variances will be explored to determine if subject may be considered a random effect. The covariance structure for the mixed models will be heterogeneous compound symmetry. If the heterogeneous compound symmetry model does not converge, then a compound symmetry structure will be used and a footnote will be added to identify the results as using a different covariance structure than usual. The kenwood-roger adjustment for the degrees of freedom will be used when calculating p-values due to the small sample size.

The maximum postdose decrease in respiratory rate (E_{max (predose - postdose)}) is the primary criterion. In addition to the primary criterion, maximum postdose reduction in SpO₂ (E_{max (predose - postdose)}) and The maximum postdose increase in EtCO₂ (E_{max (postdose - predose)}) will have the following contrasts calculated in the mixed-effects models:

- 1) Morphine + AZD4041 (Day 15) vs Morphine alone (Day 1) [Sequence 1]
- 2) Morphine + Placebo (Day 15) vs Morphine alone (Day 1) [Sequence 2]
- 3) Morphine + AZD4041 (Day 15) vs Morphine + Placebo (Day 15) [Sequence 1 vs Sequence 2]

For EtCO₂, SpO₂, and respiratory rate averages (predose average from Days 2 to 15), and postdose average on Day 15, the following contrasts will be explored in the mixed-effects models:

- 1) (postdose): Morphine + AZD4041 (postdose average Day 15) vs (predose): AZD40401 (predose average Days 2-15)

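### The two primary incidence endpoints have no planned comparative estimate, confidence interval or paired analysis; the contrasts with intervals cover only secondary measures

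*SAP*

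**What the plan says.** Protocol section 2 and SAP Table 2-1 state the primary objective as a comparison: the "effect on respiratory drive of morphine administered after multiple doses of AZD4041 compared to morphine administered alone". Two endpoints are attached to it. One is the incidence of an EtCO2 rise of 10 mmHg or more from baseline, or a value above 50 mmHg. The other is the incidence of SpO2 below 92%. Both must last 30 seconds. Every Emax and mean postdose measure is listed as secondary.

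Protocol 8.3.2.1 and SAP 9.1 plan the same analysis for these incidences. For SpO2, the incidence "will be summarized by treatment and time point using frequency tables". The EtCO2 sentence reads "of at least >50 mmHg will be summarized by treatment and time point using frequency tables". SAP 5.1 defines a categorical summary as N, n and a percentage per class.

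For inference, SAP 9.1 says that for EtCO2, SpO2 "and respiratory rate, mixed-effects models will be used for" Emax and averaged measures. The 95% intervals and p-values belong to these models. So do three contrasts for Emax: Day 15 versus Day 1 within each sequence, and AZD4041 versus placebo on Day 15. The same section calls respiratory-rate Emax the primary criterion.

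Protocol 8.5 reports no formal sample size calculation and says that the number of "participants planned for completion in this study is considered sufficient to achieve the study objectives".

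**The concern.** The question is comparative, but the endpoints chosen to answer it are only tabulated. Suppose the event definition were settled and every event captured. The plan would still give no risk difference and no interval for either primary endpoint, within Sequence 1 or between sequences on Day 15. It would also not show how many subjects changed status between the two morphine days.

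This is a safety question with a nonclinical signal behind it. Protocol 1.3.2 reports increased respiratory depression in rats when morphine followed AZD4041. Without an interval, similar percentages on the two days could mean no added effect, or too few subjects to see one. SAP 5.1 classes any analysis done after database lock or unblinding as post hoc, so an interval added then would carry less weight.

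**Working it through.** **Which endpoint gets which analysis**

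| Measure | Status in SAP Table 2-1 | Analysis in SAP 9.1 |
|---|---|---|
| Sustained EtCO2 event, incidence | Primary | Frequency table |
| Sustained SpO2 event, incidence | Primary | Frequency table |
| Emax of EtCO2, SpO2, respiratory rate | Secondary | Mixed model, contrasts, 95% CI, p-value |
| Predose and Day 15 postdose averages | Not primary | Mixed model, contrasts, 95% CI, p-value |

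**The plan's own figures.** SAP 3.4 gives six blocks: 2:2, four of 5:3, and one of 6:2. Sequence 1 is 2 + 4×5 + 6 = 28 and Sequence 2 is 2 + 4×3 + 2 = 16, total 44, as stated. Protocol 8.5 plans at least 24 + 12 = 36 completers. No event rate, power or precision is given, so all event counts below are assumptions.

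**Do the margins determine the paired answer?** Take 24 Sequence 1 completers with events in 8/24 on Day 1 and 14/24 on Day 15. The difference is 0.5833 - 0.3333 = 0.25. Let b be the number with an event on Day 15 only and c the number with an event on Day 1 only. The margins fix b - c = 6 but not b or c.

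Paired Newcombe limits, with D the difference and (l1, u1), (l2, u2) the Wilson limits for Day 15 and Day 1:

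- lower = D - √[(p1-l1)² - 2φ(p1-l1)(u2-p2) + (u2-p2)²]
- upper = D + √[(u1-p1)² - 2φ(u1-p1)(p2-l2) + (p2-l2)²]

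The Wilson limits are 0.3883 to 0.7553 for 14/24 and 0.1797 to 0.5329 for 8/24. For b:c = 6:0 the continuity-corrected φ is 0.508. The lower limit is 0.25 - √(0.0380 - 0.0395 + 0.0398) = 0.25 - 0.196 = 0.054. The other cases follow in the same way:

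| b:c | φ | 95% CI (points) | Exact McNemar p |
|---|---|---|---|
| 6:0 | 0.51 | +5 to +41 | 0.031 |
| 7:1 | 0.33 | +2 to +44 | 0.070 |
| 8:2 | 0.15 | -1 to +46 | 0.11 |
| 10:4 | -0.12 | -5 to +49 | 0.18 |
| Treated as unpaired | | -3 to +48 | Fisher 0.15 |

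Two table columns showing 8/24 and 14/24 fit all four paired rows. In the 7:1 row the interval excludes zero while the exact test does not reach 0.05, so the SAP must say in advance which of them decides.

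**Precision (Wald half-widths, assumed incidences 30% and 50%)**

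- Paired, n=24: 1.96 × √[(0.25 + 0.21 - 2φ√(0.25×0.21))/24]. This gives 23 points at φ=0.3 and 19 at φ=0.5. At these margins φ cannot exceed √(0.3/0.7) = 0.65, where the half-width is 16. If the pairing is ignored (φ=0), it is 27.
- Day 15 between sequences, 24 versus 12: 1.96 × √(0.25/24 + 0.21/12) = 33 points.
- Zero events in 24: exact two-sided upper limit 1 - 0.025^(1/24) = 14%.

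**The case against.** The best defence is that this is a Phase 1 safety study which openly has no formal sample size calculation, and that descriptive reporting of safety incidences is normal there. That stands against any demand for power or a hypothesis test. It does not explain why intervals are planned for secondary respiratory measures, and for the PK ratios in SAP 8.5.2, but not for the primary endpoints.

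A second defence is that the mixed models already answer the objective. They are repeated-measures models with a within-subject covariance structure. They contrast Day 15 with Day 1, and they cover EtCO2 and SpO2. A reader might otherwise infer that the trial has no inference on respiratory drive, or that it discards the pairing altogether. The documents do not support that: the pairing is used for Emax, and percentages per treatment are planned for the incidences. But Emax is a different quantity. It does not estimate how many subjects cross the sustained clinical thresholds, and SAP 9.1 does not say that it replaces the Table 2-1 endpoints.

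A third point stands and shapes the remedy. A paired analysis cannot assume that everyone contributes both days. About 44 are randomized for at least 36 completers, so up to 8 may lack Day 15. Protocol 6.1.15 allows withdrawal after naloxone for respiratory depression, so the missing subjects could be those with Day 1 events.

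**Conclusion.** The gap is real and should be fixed before unblinding. It is a gap in estimation, not in power. Neither document plans a comparative estimate, an interval or a paired display for the two primary incidences, and the only inference that SAP 9.1 labels primary is on a secondary endpoint.

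In the assumed example, the same pair of percentages is compatible with a lower 95% limit anywhere from -5 to +5 points. The precision figures also rest on assumed incidences, and the paired ones on an assumed correlation. They illustrate scale and are not expected values for this trial. It would go too far to infer that the numbers of subjects are inadequate, because the documents state no rate or margin against which to judge them.

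**What to change.** In SAP 9.1, for each primary endpoint, derive one yes/no per subject per morphine day using the full Table 2-1 definition. Report these with the discordant-pair counts:

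1. The Sequence 1 paired risk difference, Day 15 minus Day 1, with a paired score or Newcombe 95% CI. Name this as the main estimate for the primary objective.
2. The same for Sequence 2, and the between-sequence difference in change with a 95% CI. The latter uses both the pairing and the randomized control.
3. The Day 15 AZD4041 versus placebo risk difference with a 95% score CI.

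Base conclusions on the intervals, with exact McNemar as supportive only. Use subjects with both morphine days for the paired estimates, and report how many lack Day 15 and their Day 1 event status. Remove the statement that respiratory-rate Emax is the primary criterion, or reconcile it with Table 2-1.

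If protocol 8.5 states precision, label it as resting on assumed rates. For 30% versus 50%, it is about 16 to 23 points half-width paired at n=24, for φ from its maximum of 0.65 down to 0.3, and about 33 points for 24 versus 12.

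The cost is SAP wording and one extra table per endpoint, with no new data. The downside is that the stated precision will look modest.

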## **STUDY SYNOPSIS**

Name of	AstraZeneca AB	
Sponsor/Company:		
Name of Product:	AZD4041	
Title of Study:	A Randomized, Double-blind, Placebo-controlled, Fixed Sequence Study to Assess the Effect on Respiratory Drive of Multiple Doses of AZD4041 When Co-administered With a Single Dose of Morphine in Healthy Recreational Opioid Users	
Study Development Phase:	Phase 1	
Objectives:	Primary objective:	
	• To assess the effect on respiratory drive of morphine administered after multiple doses of AZD4041 compared to morphine administered alone in healthy recreational opioid users	
	Secondary objectives:	
	• To assess the safety and tolerability of multiple doses of AZD4041 when co-administered with a single dose of morphine in healthy recreational opioid users	
	• To assess the pharmacokinetics (PK) of AZD4041 and morphine in healthy recreational opioid users	
	• To assess the impact of multiple dose administrations of AZD4041 on the PK of morphine and its metabolites	
	
 
To assess the impact of morphine on steady-state PK of AZD4041
 
To assess the renal clearance of AZD4041
 
	
Endpoints:	Safety:	
	Primary	
	Incidence of clinically significant changes in respiratory parameters, defined as:	
	
 
Incidence of increased end tidal carbon dioxide (EtCO2) of at least 10 mmHg compared to baseline or >50 mmHg (sustained for at least 30 seconds)
 
Incidence of reduction in SpO2 to <92% (sustained for at least
 
	
	30 seconds)	
	Secondary	
	• SpO 2 (%)	
	
 
Mean time to reduction in SpO2 to <92% (sustained for at least 30 seconds)
 
	
	
 
Mean duration of reduction in SpO2 to <92% (sustained for at least 30 seconds)
 
	

 
Maximum postdose reduction of SpO2 adjusted for baseline
 

 
Mean postdose SpO2
 

• EtCO 2 (mmHg)

 
Mean time to each increased EtCO2 episode of at least 10 mmHg compared to baseline or >50 mmHg (sustained for at least 30 seconds)
 

 
Mean duration of each increased EtCO2 episode of at least 10 mmHg compared to baseline or >50 mmHg (sustained for at least 30 seconds)
 

 
Maximum postdose increase in EtCO2 adjusted for baseline
 

 
Mean postdose EtCO2
 

• Respiratory rate (breaths/min)

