# 8.3.1. Safety Endpoints

The primary safety endpoints are:

- Incidence of increased EtCO2 of at least 10 mmHg compared to baseline or >50 mmHg (sustained for at least 30 seconds)
- Incidence of reduction in SpO2 to <92% (sustained for at least 30 seconds)

The secondary safety endpoints are:

- Mean time to reduction in SpO2 to <92% (sustained for at least 30 seconds)
- Mean duration of reduction in SpO2 to <92% (sustained for at least 30 seconds)
- Maximum postdose reduction of SpO2 adjusted for baseline
- Mean postdose SpO2
- Mean time to each increased EtCO2 episode of at least 10 mmHg compared to baseline or >50 mmHg (sustained for at least 30 seconds)
- Mean duration of each increased EtCO2 episode of at least 10 mmHg compared to baseline or >50 mmHg (sustained for at least 30 seconds)
- Maximum postdose increase in EtCO2 adjusted for baseline
- Mean postdose EtCO2
- Incidence of reduced respiratory rate to <6 breaths/min (sustained for at least 30 seconds)
- Mean time to each reduced respiratory rate episode of <6 breaths/min (sustained for at least 30 seconds)

- Mean duration of each reduced respiratory rate episode of <6 breaths/min (sustained for at least 30 seconds)
- Maximum postdose decrease in respiratory rate adjusted for baseline
- Mean postdose respiratory rate
- Incidence, frequency, severity and relationship of AEs
- Vital signs measurements (BP, HR, and oral temperature)
- ECGs (12-lead safety ECGs, 12-lead dECGs, and ECG telemetry)
- Clinical laboratory test results (clinical chemistry, hematology, coagulation, urinalysis)
- Physical examination findings
- Type of medical intervention used, summarized for each event of significantly increased EtCO2, reduced SpO2 or respiratory rate

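### SAP 9.1 names a secondary variable as the primary criterion and drops the 10 mmHg limb from the EtCO2 primary endpoint

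*SAP*

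**What the plan says.** **Endpoint definitions.** The protocol Synopsis introduces the primary endpoint as "Incidence of clinically significant changes in respiratory parameters, defined as" and lists two items: sustained EtCO2 elevation and sustained SpO2 below 92%. Protocol Section 2 lists the same two. Protocol 8.3.1 repeats them after the words "The primary safety endpoints are". SAP Table 2-1 agrees, and gives the first as "EtCO₂ (mmHg): Incidence of increased EtCO₂ of at least 10 mmHg compared to baseline or >50 mmHg (sustained for at least 30 seconds". In all four places "Maximum postdose decrease in respiratory rate adjusted for baseline", or its equivalent, stands among the secondary endpoints.

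**Analysis text.** SAP 9.1 says of the mixed-model variables: "The maximum postdose decrease in respiratory rate (E_{max (predose - postdose)}) is the primary criterion". The next sentence begins "In addition to the primary criterion, maximum postdose reduction in SpO₂" and goes on to EtCO2, so both are presented as additions to respiratory rate. For the EtCO2 events SAP 9.1 says: "Incidence of increased EtCO₂ of at least >50 mmHg will be summarized by treatment and time point using frequency tables". Time to episode and duration of episode are worded with the same single limit. For SpO2 it says: "Incidence of reduction in SpO₂ to <92% will be summarized by treatment and time point using frequency tables". The 30-second condition appears nowhere in the section. Protocol 8.3.2.1 has the same 50 mmHg wording and the same omission of 30 seconds, but it ranks none of the three Emax measures above the others.

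**The concern.** Section 9.1 is the text from which the tables will be programmed and the results ordered. It conflicts with the endpoint definitions in two ways.

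First, it gives the title of primary to a variable that belongs to neither primary endpoint. A report that follows it would lead with respiratory-rate Emax, while one that follows Table 2-1 would lead with the two incidences.

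Second, a literal reading counts an EtCO2 event only above 50 mmHg. A subject whose EtCO2 rises by 10 mmHg or more but stays at or below 50 mmHg meets the primary endpoint as defined, yet would be missing from its incidence, time-to-episode and duration summaries. In a study that asks whether AZD4041 worsens morphine's effect on breathing, that is an undercount of primary safety events.

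SAP 5.1 treats as a priori only what is defined before database lock and/or unblinding. If the conflict stays, somebody will have to choose between the versions later.

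**Working it through.** The documents state no alpha, power or sample-size calculation to reproduce (protocol 8.5, SAP 3.5). The core of the check is a comparison of texts.

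| Place | Primary | Respiratory-rate Emax | EtCO2 event | 30 seconds |
|---|---|---|---|---|
| Protocol Synopsis, Section 2, 8.3.1 | EtCO2 and SpO2 incidence | secondary | rise of at least 10, or >50 mmHg | yes |
| SAP Table 2-1 | EtCO2 and SpO2 incidence | secondary | rise of at least 10, or >50 mmHg | yes |
| Protocol 8.3.2.1 | not ranked | not ranked | >50 mmHg only | no |
| SAP 9.1 | respiratory-rate Emax | primary criterion | >50 mmHg only | no |

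The Amendment 01 summary records only the morphine supply change and exclusion criterion 23, so no logged endpoint change explains the difference. The capnography alarm rule in protocol 6.1.14 uses whichever EtCO2 limit is lower, so monitoring would flag events that the literal analysis text leaves out.

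**Where the missing limb bites.** The limit under the full definition is the lower of baseline + 10 and 50 mmHg, so the 10 mmHg limb is the easier one whenever baseline is below 40 mmHg. Protocol 6.1.9 gives two site cohorts, mean 36.6 (SD 2.2, N=8) and mean 36.1 (SD 3.88, N=15), and an expected baseline range of 34 to 48 mmHg.

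Rise needed to pass 50 mmHg, against 10 mmHg under the full definition:
- baseline 36.6: 50 − 36.6 = 13.4
- baseline 36.1: 50 − 36.1 = 13.9
- baseline 34: 50 − 34 = 16

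Share of subjects starting below 40 mmHg, if baseline is normal:
- Φ((40 − 36.6)/2.2) = Φ(1.545) = 0.939
- Φ((40 − 36.1)/3.88) = Φ(1.005) = 0.843

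With the normal distribution cut to 34–48 mmHg the shares are 0.931 and 0.778.

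**How many events could be lost.** The documents give no distribution of the peak rise, so this part rests on assumption. Take the peak sustained rise as normal, independent of baseline, with SD 3, 4 or 5 mmHg. The share of full-definition subjects missed is

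1 − P(peak > 50) / P(rise ≥ 10 or peak > 50),

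integrated over baseline. For example, with baseline 36.6 (SD 2.2), mean rise 10 and SD 5: 1 − 0.267/0.505 = 0.47. The ranges below cover the three SDs and both cohorts.

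| Assumed mean rise (mmHg) | Missed, baseline uncut | Missed, baseline cut to 34–48 |
|---|---|---|
| 6 | 55–76% | 40–73% |
| 10 | 47–64% | 33–60% |
| 14 | 31–45% | 22–32% |
| 20 | 4–15% | 2–7% |

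The loss shrinks as the rise grows. Protocol 1.3.2.1 calls the morphine dose supratherapeutic, so the lower rows cannot be ruled out.

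**The case against.** The strongest reply is that both points are loose wording. The term primary criterion is not defined, and it sits between the model specification and the Emax contrasts, so it may mean only the lead variable among the modelled measures. Table 2-1 ranks the endpoints correctly, and no error rate or sample size hangs on the label. The EtCO2 phrase is ungrammatical, looks like a truncation and is carried over from protocol 8.3.2.1. The full definition stands elsewhere, alarms use both limits, and alarms are reported as AEs where applicable. Leaving out the 30 seconds may be mere abbreviation.

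Part of this stands. The label's harm is limited to which result is reported as primary. The 30-second omission is closer to shorthand than to contradiction. Larger EtCO2 rises would still show in the Emax summaries and possibly as AEs.

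The rest does not. No text gives the lead-variable reading, and that reading would still put respiratory rate ahead of the two parameters that are primary. The 50 mmHg wording recurs for incidence, time and duration in both documents, and nothing in either analysis section restores the other limb. A programmer who follows SAP 9.1 as written would produce the wrong primary table.

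It is also fair that the missed shares rest on chosen values and that the baseline cohorts are small. The conclusion does not depend on those shares.

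**Conclusion.** The concern holds on both counts, and the text must be corrected. SAP 9.1 contradicts SAP Table 2-1 and protocol Sections 2 and 8.3.1 on which result is primary. Read literally, it also replaces the EtCO2 primary endpoint with a narrower one.

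The label affects reporting order only. The definition affects the primary count: from the site's mean baselines it raises the required rise from 10 to more than 13.4 or 13.9 mmHg, and it matters for the 94% and 84% of subjects who start below 40 mmHg (93% and 78% with baselines cut to the expected range). Those shares assume normal baselines like those of two cohorts of 8 and 15. The number of events lost runs from a few percent to about three quarters, depending on a peak rise that the documents do not give. The severity rests on the contradiction in the text.

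**What to change.** **In SAP 9.1:**
1. Remove both mentions of a primary criterion. List the three Emax measures as secondary endpoints and keep the three contrasts as they are.
2. State that the EtCO2 and SpO2 incidence endpoints are primary.
3. Replace the 50 mmHg wording with the full Table 2-1 definition (both limbs and the 30-second condition) for EtCO2 incidence, time and duration. Restore the 30-second condition for SpO2 and respiratory rate.

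**In the protocol:** reconcile 8.3.2.1 with Sections 2 and 8.3.1.

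**Cost.** The SAP changes are wording only, to be made before database lock, with no new tables. Protocol 12.2 sends protocol amendments to the IRB, so aligning 8.3.2.1 carries that step; the SAP can be corrected meanwhile by citing Sections 2 and 8.3.1. Protocol 6.1.14 already requires events to be timed, but confirm that the episode times reach the database, because spot readings cannot show 30-second persistence.

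**Optional, and not an error correction.** The protocol plans frequency tables for incidence and keeps inference for Emax. Since the primary objective is comparative, per-subject incidence on each morphine day could be added with 95% intervals for the differences: Day 15 against Day 1 paired within sequence, and Sequence 1 against Sequence 2 on Day 15. Treat these as estimation only. Precision at 24 and 12 completers is low: with no events, the exact upper 95% limits are 14.2% and 26.5%.
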